7.5.4 Vital Signs and Physical Measurements

For each vital sign parameter (systolic blood pressure, diastolic blood pressure, pulse rate, respiratory rate, temperature) and physical measurement parameter (weight, BMI), observed values and changes from baseline will be summarized at the following timepoints: baseline, each scheduled visit, early termination, and Follow-up visit using SS. See Section 7.2.2 for handing multiple values in an analysis window.

The number and percentage of participants with vital sign abnormalities in the following categories will be presented during the treatment (using SS) and follow-up (using FUSS) safety analysis periods, respectively, for participants in different categories of average rimegepant exposure (< 2 , ≥ 2 to < 8 , ≥ 8 to < 14 , < 14 and ≥ 14 tablets per month) and overall participants:

Individual listing will be provided using SS.

Systolic BP (mm Hg)	min. < 90	
Systolic BP (mm Hg)	max. > 140	
Systolic BP (mm Hg) change from baseline	max. decrease ≥ 30	max. increase ≥ 30
Diastolic BP (mm Hg)	min. < 50	
Diastolic BP (mm Hg)	max. > 90	
Diastolic BP (mm Hg) change from baseline	max. decrease ≥ 20	max. increase ≥ 20
Pulse rate (beats/min)	min. < 40	max. > 120

7.5.5 12-lead ECG

For each 12-lead ECG parameter (heart rate, PR interval, QRS duration, QT interval, and QTcF), the observed values and changes from baseline will be summarized at the following timepoints: baseline, each scheduled visit, early termination, and Follow-up visit using SS. See Section 7.2.2 for handing multiple values in an analysis window.

The number and percentage of participants with ECG abnormalities in the following categories will be presented during the treatment safety (using SS) and follow-up (using FUSS) safety analysis periods, respectively, for participants in different categories of average rimegepant exposure (< 2, \geq 2 to < 8, \geq 8 < 14, \geq 14 and \geq 14 tablets per month) and overall participants:

- QTcF (msec): \leq 450, 450 - \leq 480, 480 - \leq 500, $>$ 500
- QTcF increase from baseline (msec): \leq 30, 30 - \leq 60, $>$ 60.

Individual listing will be provided using SS.

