#### **3.2. Study Endpoints**

##### **3.2.1. Primary Endpoints**

- Adverse events, common adverse events (incidence  $\geq 5\%$ ), serious adverse events, adverse events leading to study drug discontinuation, etc.; ECG, vital signs/physical measurements and clinical laboratory test abnormalities.

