### **5) ECG and Clinical Laboratory Test Findings**

- a) Estimated glomerular filtration rate (eGFR)  $\leq 40 \text{ mL/min/1.73 m}^2$  according to the re-expressed abbreviated (four-variable) Modification of Diet in Renal Disease (MDRD) study equation;

- b) Corrected QT interval  $> 470$  msec (QTc by method of Frederica) at Screening;
- c) Left Bundle Branch block;
- d) Right Bundle Branch Block with QRS duration  $\geq 150$  msec;
- e) Intraventricular Conduction Defects with QRS duration  $\geq 150$  msec;
- f) Serum bilirubin (Total, Direct or Indirect)  $> 1 \times$  ULN (Only abnormal values of between  $1-1.5 \times$  ULN may be repeated once for assessment of eligibility during the screening period);
- g) Neutrophil count  $\leq 1000/\mu\text{L}$  (or equivalent);
- h) AST or ALT  $> 1 \times$  ULN (Only abnormal values of between  $1-1.5 \times$  ULN may be repeated once for assessment of eligibility during the Screening Period.);
- i) Glycosylated hemoglobin (HbA1c)  $> 7\%$ .

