#### **6.1.3. Electrocardiogram (ECG)**

A standard 12-lead ECGs will be performed at the Screening Visit, Baseline Visit, scheduled site visits (Week 28, 52, or early termination), and Safety follow up Visit as specified in [Table 1](#).

ECG examination indicators mainly include heart rate, PR interval, QRS duration, QT interval and QTc interval.

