### **10.5.2. Safety Analysis**

The primary endpoints of this study are adverse events, common adverse events (incidence  $\geq 5\%$ ), serious adverse events, adverse events leading to study drug discontinuation, etc.; ECG, vital signs/physical measurements and clinical laboratory test abnormalities.

Adverse events will be coded using the Medical Dictionary for Regulatory Activities (MedDRA). Analysis of adverse events will be mainly based on TEAEs. All TEAEs, common TEAEs (incidence  $\geq 5\%$ ), SAEs, and TEAEs leading to study drug discontinuation will be summarized and analyzed by SOC and PT, and the AEs will be listed by participant.

Vital signs/physical measurements, ECG parameters, and laboratory tests and their changes from baseline will be summarized by visit using descriptive statistics. The number and percentage of participants with abnormal ECG, vital signs, and laboratory test (according to CTCAE grade) will be presented. LFT elevations will also be summarized with number and percentage of participants in pre-specified categories. In addition, these safety data will also be listed by participant.

Additional details can be found in the SAP.

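### ECG abnormalities are part of the primary endpoint, but the SAP's ECG-abnormality table counts QTcF only; PR, QRS and ECG heart rate have no count of their own

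*SAP*

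**What the plan says.** Protocol 3.2.1 places "ECG, vital signs/physical measurements and clinical laboratory test abnormalities" in the primary endpoint beside adverse events. SAP 4.1 repeats this, and neither document singles out an ECG parameter. Protocol 10.5.2 commits to a count: "The number and percentage of participants with abnormal ECG, vital signs, and laboratory test (according to CTCAE grade) will be presented". It leaves further detail to the SAP. On measurement, Protocol 6.1.3 states: "ECG examination indicators mainly include heart rate, PR interval, QRS duration, QT interval and QTc interval".

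SAP 7.5.5 handles the ECG in two ways:

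- **By-visit summaries.** "For each 12-lead ECG parameter (heart rate, PR interval, QRS duration, QT interval, and QTcF), the observed values and changes from baseline" are summarised at baseline, each scheduled visit, early termination and follow-up.
- **Abnormality counts.** "The number and percentage of participants with ECG abnormalities in the following categories will be presented", for the treatment and follow-up safety periods and by exposure category. Two categories follow: QTcF value, with cut-points at 450, 480 and 500 msec, and "QTcF increase from baseline (msec)", with cut-points at 30 and 60 msec.

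An individual listing completes the section. It gives no limit, normal/abnormal category or shift table for heart rate, PR or QRS.

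**The concern.** The endpoint and the protocol's analysis commitment speak of ECG abnormality in general. The table that is meant to deliver it covers one parameter, and the SAP gives no reason for the narrowing. A summary by visit describes a distribution. It does not say how many participants crossed a limit during treatment, or whether they were already beyond it at baseline, and an abnormality endpoint exists to answer those two questions.

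Conduction is also something the protocol already treats as a safety matter. The entry criteria exclude left bundle branch block, "Right Bundle Branch Block with QRS duration" of 150 msec or more, and intraventricular conduction defects with the same QRS limit. Conduction findings of those kinds on treatment should therefore mostly be new, yet no ECG table is set up to count them.

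What is at stake is the completeness of one component of the primary endpoint. Findings that the investigator does not judge clinically significant would be left out of any count for PR and QRS. For heart rate they would be counted only if the pulse also passed the vital-sign limits.

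**Working it through.** This is a comparison of texts, with a little arithmetic for scale.

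**Step 1. The plan's own safety figure.** Protocol 10.2 and SAP 3.4 give the probability of seeing at least one event among 240 participants as above 99.9% at a true rate of 5%, and 91.0% at 1%. The formula is 1 − (1 − p)^240.

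- p = 0.05: 1 − 0.95^240 = 99.9995%
- p = 0.01: 1 − 0.99^240 = 91.04%

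Both agree with the documents. The point below does not depend on them.

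**Step 2. Which objective measures are counted as abnormal, and where.**

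| Measure | Count of participants with an abnormality | Other planned output |
|---|---|---|
| Laboratory tests (SAP 7.5.3) | All CTCAE-graded tests, with shifts from baseline; liver tests by multiples of ULN | By-visit summaries, listings |
| Vital signs (SAP 7.5.4) | Systolic and diastolic pressure, value and change; pulse <40 and >120 | By-visit summaries, listing |
| QTcF (SAP 7.5.5) | Value and increase categories | By-visit summaries, listing |
| PR, QRS (SAP 7.5.5) | None | By-visit summaries, listing |
| ECG heart rate (SAP 7.5.5) | None | By-visit summaries, listing |

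Uncorrected QT also has no category, but QTcF reasonably stands in for it. Three of the five indicators in Protocol 6.1.3 are left without a count in the ECG table.

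**Step 3. What other tables pick up.**

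- Protocol 8.1 makes an abnormal ECG an adverse event when the investigator judges it clinically significant. SAP 7.5.2 tabulates adverse events by SOC and PT as number and percentage.
- The pulse limits in SAP 7.5.4 partly cover heart rate.
- SAP 7.1 includes minimum and maximum among the descriptive statistics, so the by-visit tables may show an extreme PR, QRS or heart-rate value, or an extreme change.

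**Step 4. What remains uncounted.** A by-visit maximum is one value. At a true rate of 1%, the expected number affected is 240 × 0.01 = 2.4 participants, and the maximum cannot tell one from three. It also does not show the same participant's baseline status. SAP 7.5.5 summarises scheduled visits, early termination and follow-up. Under SAP 7.2.2, the last of several readings at a visit is the one summarised, and unscheduled results are shown in the listings. An extreme value on an unscheduled ECG, or on an earlier repeat, could therefore miss the by-visit tables.

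**Step 5. Scale.** Each affected participant is 1/240 = 0.42% of the planned sample. On-treatment ECGs are scheduled only at Weeks 28 and 52 or early termination, so the denominator with a post-baseline ECG may be smaller than 240.

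**The case against.** The strongest reply is that nothing in the SAP contradicts the protocol. Protocol 10.5.2 names no ECG parameter or threshold and defers to the SAP, and the SAP answers with QTcF. Protocol 6.1.3 says what is measured; it does not promise an abnormality category for each measure. The study is descriptive and tests no hypothesis. This stands to the extent that the SAP may choose the cut-points. It does not explain why the broad endpoint is restated in SAP 4.1 while three measured indicators drop out of the count, when laboratory tests and vital signs are counted on several parameters.

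A reader might go further and infer that new heart-rate, PR or QRS abnormalities appear in no incidence table at all. The documents do not support that: clinically significant findings reach the adverse-event tables, and the pulse limits catch extreme rates.

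A reader might also argue that single cases would be hidden because a mean barely moves. As an assumed example, if one participant in 240 goes from a QRS of 90 to 150 msec, the mean shifts by (150 − 90)/240 = 0.25 msec. That argument fails as well. If the change is seen at a summarised visit, the same table would show a maximum of at least 150 msec and a maximum change of at least 60 msec.

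The adverse-event table still does not replace the missing count. The endpoint lists adverse events and ECG abnormalities as separate components, and reporting an ECG change as an adverse event rests on investigator judgement in an open-label, single-arm trial.

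**Conclusion.** The point holds in a limited form. The SAP 7.5.5 abnormality table covers QTcF only. PR and QRS abnormalities are counted only as adverse events, and heart-rate abnormalities only as adverse events or through the pulse limits. Extremes may be visible by visit, but the number of participants affected and whether the finding was new are not reported. This is a gap between a primary endpoint component and its analysis, partly covered elsewhere. It is not an arithmetic error, and no stated figure changes.

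The conclusion assumes that the two QTcF bullets are the complete list of categories in SAP 7.5.5. How often uncounted abnormalities will occur cannot be judged from the documents. The change is worth making because it completes a primary endpoint component from measurements already collected.

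**What to change.** Before database lock, add to the existing SAP 7.5.5 treatment and follow-up tables the number and percentage of participants with a post-baseline abnormality not present at baseline, for QRS, PR and ECG heart rate.

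- **Limits.** Write them into the SAP. For QRS, 150 msec or more is one example. It comes from the entry criteria, where it applies to right bundle branch block and intraventricular conduction defects, so it would serve here as a reporting limit only. The documents give no limits for PR or ECG heart rate, so the sponsor must specify them.
- **Denominator.** State it as participants with a baseline and at least one post-baseline value in the period.
- **Same sentence.** The exposure strata in SAP 7.5.5 read ≥14 twice, where the other safety tables have <14 and ≥14. Check and correct this in the same edit.

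The cost is a few more rows in planned tables and slightly longer output. No new data collection is needed.

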7.6 COVID-19-related Visit Impact

A listing of enrolled participants with visits impacted by COVID-19 will be provided. The listing will contain the following information: “What was the impact?”, “How was the impact related to COVID-19?”, and “Did the participant withdraw from the study due to COVID-19?”.

8 APPENDIX

8.1 The Derivation of Migraine Day

Migraine Day Derivation

eDiary logs with all evening questions and follow-up questions being empty will be deleted.

A migraine day is defined as an eDiary day with either (I) or (II):

I. Qualified migraine headache based on all the following criteria (a and b):

a. Lasting for \geq 30 minutes:

i. Headache duration

= (1) Headache end time# – headache start time#, where headache start and end dates (with “ENDED” to the question about headache status) are the same, and eDiary entry date is on the same date;

= (2) Headache end time# – headache start time#, where headache start and end dates (with “ENDED” to the question about headache status) are the same, but eDiary entry date is later than the headache start date;

= (3) Headache end time# – 0 o’clock of the headache end date, where headache end date (with “ENDED” to the question about headache status) is later than the

headache start date, and eDiary entry date is later than the headache start date but could be either equal to or later than the headache end date.

= (4) Headache end time# – 0 o'clock of the headache end date, where headache start date is missing, headache end date (with "ENDED" to the question about headache status) is available and eDiary entry date is either equal to or later than the headache end date, and follow-up log is not available.

ii. Headache-to-entry duration

= (1) eDiary entry time# – headache start time#, where headache start and eDiary entry dates are the same, and headache end time# is missing (not answered or "STILL CONTINUING" to the question about headache status);

= (2) eDiary entry time# – 0 o'clock of the entry date, where eDiary entry date is later than the headache start date, and headache end time# is missing (not answered or "STILL CONTINUING" to the question about headache status).

iii. Headache-to-FU duration

= follow-up log headache end time@ or follow-up log entry time@ – headache start time#, where follow-up headache log is available with a headache end time or a follow-up log entry time if headache end time is missing.

vi. Define an eDiary reference date to be the eDiary entry date for scenarios i (1), ii (1), ii (2), and headache start date for scenarios i (2), iii, iv, and headache end date for scenario i (3) and i (4) . A migraine day will be identified based on the eDiary reference date.

b. Meeting at least one of the following criteria (i or ii):

- ≥ 2 of the following pain features based on “yes” response to questions with the same eDiary reference date/time:
 - Unilateral location#,
 - Pulsating quality (throbbing)#,
 - Moderate or severe pain intensity#
 - Aggravation by or causing avoidance of routine physical activity (e.g. walking or climbing stairs)#
- ≥ 1 of the following associated symptoms based on “yes” response to questions with the same eDiary reference date/time:
 - Nausea#
 - Vomiting#
 - Both photophobia# and phonophobia#

II. Taking triptan, ergotamine or study medication: “Yes” response to the question about taking triptan to treat headache or during aura #@, question about taking ergotamine to treat headache or during aura #@, or question about taking study medication to treat headache or during aura #@@& in the LTT analysis period.

Note that data marked with “#” are identified from the evening headache log; data marked with “@” are identified from the follow-up headache log; data marked with “&” are identified from drug administration information collected via CRF.

III. After a migraine day is derived based on steps I and II for each log, the logs with duplicated eDiary reference date will be deduped by keeping the original log if both original log and added log are on the same reference date, followed by keeping the one with migraine day identification=YES, next followed by keeping the most severe migraine, and then followed by keeping the log with the latest headache end date.

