#### **4.3.1. Screening Visit, Observation Period (30 days ±2 days)**

The participant or his/her guardian must sign the informed consent form voluntarily in writing before participating in the screening. Approximately 330 participants will be screened for this study to allow approximately 240 participants to receive treatment of rimegepant.

The main procedures or tests to be completed by the participant at the Screening Visit include:

- Signing the informed consent form;
- Evaluation of inclusion/exclusion criteria;
- Collection of migraine history (signs/symptoms/frequency/intensity) and other medical history;
- Serum virological examination;
- Demographic information;
- Physical examination;
- Vital signs/physical measurements;
- Clinical safety laboratory tests;
- ECG;
- Urine routine;
- Urine drug screen;
- FSH (if applicable);
- Urine pregnancy;
- AE and SAE assessments;
- Dispense eDiary
- Install BYOD APP in the participant mobile phone.

The eDiary will be dispensed and BYOD APP will be installed after the participant has completed all screening procedures at the Screening Visit and the eDiary will be used to record migraine attacks and their severity on a daily basis during the Observation Period, as well as whether they received migraine treatment. BYOD will be used to record prophylactic or standard of care migraine medications/concomitant medications. Participants will be

trained in the use of eDiary and BYOD. Height in the physical measurements will only be measured at the Screening Visit. If a participant's WOCBP status has been confirmed in the BHV3000-310 trial, the participant is recognized to have the same status in this study and a repeat FSH test is not required.

During the Observation Period (30 days  $\pm 2$  days), the main procedures or examinations to be completed by the participant include:

- Recording prophylactic and standard of care migraine medications/concomitant medications via BYOD;
- AE and SAE assessments;
- Daily recording of migraine attacks and their severity by eDiary.

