## 5.5. Prophylactic and Standard of Care Migraine Medications

Participants using prophylactic migraine medications are permitted to remain on therapy if the dose has been stable for at least 2 months prior to the Baseline Visit and this dose is not expected to change during the study. Participants who previously discontinued prophylactic migraine medication must have done so at least 5 half-lives of the prophylactic medication prior to the Screening Visit.

Participants may need to take previously prescribed standard of care medications: aspirin, ibuprofen, acetaminophen (including Excedrin®Migraine) up to 1000 mg/day for a maximum of 2 consecutive days at a time, naproxen (or any other type of non-steroidal anti-inflammatory [NSAID]), antiemetics (eg, metoclopramide or promethazine), or muscle relaxants, which are used during the study (Observation Period and Long-Term Treatment Phase) for the standard of care treatment of migraine.

Use of triptans by participants without a contraindication to their use is allowed during the Observation Phase but must be discontinued at the Baseline Visit. As described above, use of triptans is prohibited during the Long-Term Treatment Phase. With the exception of triptans described in this section, participants are allowed to take standard treatment for migraine during the study, if needed, but are required to meet dose restrictions if taking acetaminophen (no more than 1000 mg/day at a time for 2 consecutive days).

If a participant takes a tablet of study drug and experiences a migraine later that day, the participant can take standard of care medications for migraine (as described in this section above) after taking the study drug that day. Participants are not allowed to take more than 1 tablet of the study medication per calendar day.

Use of standard of care medications during Observation Period and Long-Term Treatment Phase, will be recorded by the participant via BYOD and reported to the site.

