7.2.3 Derived Dates

Study Days

Refer to Protocol Section 4.3 for the schedule of assessments. Study Days are calculated from the LTT start date as follows:

- Assessment/event date/eDiary reference date – LTT start date + 1, if the assessment/event date \geq LTT start Date;
- Assessment/event date/eDiary reference date – LTT start date, if the assessment/event date $<$ LTT start Date, where

LTT start date is defined as earlier of (1) Baseline Visit date, or (2) study drug start date (see also in Section 7.2.4).

Treatment Days

Treatment days are calculated from the study drug start date as follows:

- Assessment/event date – study drug start date + 1, if the assessment/event date \geq study drug start date.
- Assessment/event date – study drug start date, if the assessment/event date $<$ study drug start date.

The Treatment Day will be displayed together with Study Day in the individual participants listings.

eDiary Days

An eDiary day is defined as a day with a complete eDiary reference date based on any question from the evening report headache log or follow up log (see step b.iv in [Appendix: the derivation of migraine day](#)).

Last Contact Date

The last contact date is used to determine select parameters (i.e., time on study, imputed non-study medication end dates), and is typically defined using non-imputed dates as follows:

1. Earliest complete death date from all sources that collect death dates (e.g., Death CRF), if it exists.
2. Otherwise, the maximum complete date of the following CRF or external data sources, as applicable: AE start or end; ECG; eDiary assessment; informed consent; laboratory test collection; non-study medication start or end; physical exam; protocol deviation;

questionnaire; rating scale; study intervention start or end; participant disposition completion/discontinuation; visit; vital signs.

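### Study-drug days in the treatment period have a second, non-diary source, while triptan days in the Observation Period rest on the diary alone, so the change from OP can understate the reduction

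*SAP*

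**What the plan says.** SAP 8.1 opens the derivation with "A migraine day is defined as an eDiary day with either (I) or (II"), where (I) is a qualifying headache and (II) is use of a migraine-specific drug. SAP 7.2.3 sets the gateway: "An eDiary day is defined as a day with a complete eDiary reference date based on any question from the evening report headache log" or from the follow-up log.

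Step II names three drugs and attaches source marks to each. The marks # and @ stand for the evening and follow-up diary logs; & stands for data that "are identified from drug administration information collected via CRF".

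- Triptan: "question about taking triptan to treat headache or during aura", marked # and @.
- Ergotamine: "question about taking ergotamine to treat headache or during aura", marked # and @.
- Study drug: "question about taking study medication to treat headache or during aura #@@& in the LTT analysis period".

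Protocol 5.5 says that triptan use by participants without a contraindication "is allowed during the Observation Phase but must be discontinued at the Baseline Visit"; Protocol 5.4 prohibits triptans in the Long-Term Treatment Phase. The OP also has a second medication record: under Protocol 4.3.1, "BYOD will be used to record prophylactic or standard of care migraine medications/concomitant medications". Protocol Appendix 2 applies one medication rule to study drug, triptan and ergotamine, and Protocol 6.2.1 names only eDiary data as the basis for migraine days.

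**The concern.** The secondary endpoint is the LTT count minus the OP count, each prorated to 28 days (SAP 7.4.1). A source that is searched in one period and not in the other does not cancel in that difference. Study drug, the migraine-specific drug of LTT, is looked up in the diary and in the dosing CRF. Triptans, which belong to the OP, are looked up in the diary only. A triptan day that appears on BYOD but not in the diary can be lost from the OP, while the equivalent study-drug day is kept in LTT.

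The records can plausibly differ. Study-drug doses are entered on BYOD, separately from the eDiary, and Protocol 7.4 has them checked against returned tablets, with missing doses corrected. No comparable reconciliation is described for triptans. A loss of OP days would make the reduction look smaller than it is, and would carry into the confidence intervals and the responder percentages in SAP 7.4.1.

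**Working it through.** **The plan's own figures.** The planning change is 8.84 − 9.92 = −1.08 days, with SD 4.74 (Protocol 10.2, SAP 3.4). A one-sample t calculation at one-sided 2.5% gives 205 evaluable participants for 90% power (90.1%), and 205 / 0.88 = 233 after 12% dropout. Both match the documents. The present point leaves them unchanged; −1.08 serves only as a yardstick.

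**Sources by period (SAP 8.1 step II; Protocol 5.4, 5.5).**

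| Drug | OP | LTT | Unequal? |
|---|---|---|---|
| Triptan | diary logs | prohibited | OP side: diary only |
| Study drug | not taken | diary logs + dosing CRF | LTT side: diary + CRF |
| Ergotamine | diary logs | diary logs | no |

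The imbalance is triptan in OP against study drug in LTT. Ergotamine has the same source in both periods and contributes nothing.

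**When the source matters.** A non-diary record changes the count only if all three conditions hold:

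1. the day is an eDiary day;
2. the headache does not already qualify under step I;
3. the diary log does not report the drug.

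Proration is 28 × migraine days / eDiary days. Such a day moves the numerator by one and leaves the denominator alone.

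**Error against Appendix 2.** Appendix 2 counts a calendar day on which the drug was taken for headache or during aura, whatever record shows it. A CRF-found study dose of that kind is a proper migraine day. The error is therefore the OP triptan days that are missed.

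Let t be triptan days per 28 in the OP, and f the share of them that meet the three conditions and are found only outside the diary. The OP shortfall is t × f, and the change (LTT − OP) moves up by the same amount. Neither t nor f is in the documents; t = 3 and the values of f are assumptions.

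| f | OP days missed (3f) | Share of 1.08 | −1.08 would appear as |
|---|---|---|---|
| 2% | 0.06 | 6% | −1.02 |
| 5% | 0.15 | 14% | −0.93 |
| 10% | 0.30 | 28% | −0.78 |

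If f = 0, the error is zero.

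**Would diary-only in both periods be cleaner?** Assume also 8 study-drug days per 28 in LTT and the same f. Diary-only capture loses 8f from LTT and 3f from OP, so the change moves by −8f + 3f = −5f: −0.10, −0.25 or −0.50 days. On these assumptions that error is larger than the 3f above and favours the drug.

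**The case against.** The strongest reply is that the dosing CRF is a sound source for study drug. Each tablet must be recorded on BYOD and doses are checked against returns, so using that record makes the LTT count more complete, not wrong. This stands, and it is why the remedy lies on the OP side.

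A reader might infer more than the text supports, in four ways:

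- **That the change is biased.** The documents show unequal sources, not disagreement between them. If the OP diary misses no triptan day, or the missed days already qualify under step I, nothing changes.
- **That every dose recorded outside the diary becomes an LTT migraine day.** It does not: the day must be an eDiary day.
- **That the size is 8f.** With 8 study-drug days this would be 0.16, 0.40 or 0.80 days, or 15%, 37% or 74% of 1.08. Those figures treat LTT days that Appendix 2 counts correctly as error.
- **That ergotamine adds to the imbalance.** Its source is the same in both periods.

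Another fair objection concerns the remedy. SAP 7.2.1 and 7.3.6 handle non-study medications by start and end dates, with imputation. If triptans are held as intervals, merging them could create false OP migraine days and inflate the reduction. This stands as a condition on the fix.

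Finally, items iv and v of step I.a are not in the text available, and the study-drug mark carries a doubled symbol, so some caution on exact operation is due. Step II and its key to the marks are readable, and nothing visible there gives triptans a second source.

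**Conclusion.** The unequal capture is in the text, and neither document gives a reason for it. It can understate the reduction from OP. That is the conservative direction, and it affects a secondary endpoint reported descriptively without formal testing; the primary safety endpoints are untouched. The documents do not allow the size to be estimated. On an assumed 3 triptan days per 28 with 2% to 10% found only outside the diary, it is 0.06 to 0.30 days, or 6% to 28% of the planning change. It deserves a correction because this is the only secondary endpoint, its planning change is about one day, and the data for a more even derivation may already be in hand.

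**What to change.** - **Sources.** In SAP 8.1 step II, add BYOD/CRF triptan and ergotamine records as a source in both periods. Use them on eDiary days only, and only where the record shows use on a specific calendar day for headache or during aura. Exclude start-to-end intervals and imputed dates.
- **Transparency.** Report, for OP and for LTT, the number of migraine days that rest only on a non-diary record. This shows directly whether the issue matters.
- **Sensitivity.** Add a supportive analysis using diary answers only, for all three drugs in both periods. State beside it that it may undercount LTT days more than OP days and so err in favour of the drug.

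The cost is SAP wording and a small amount of programming on records the protocol already collects. The downside is that records without day-level dates cannot be used, so some imbalance may remain.
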